**Pharmacokinetics and Pharmacodynamic Data
Analysis Plan PART 1**

For

PROTOCOL: NCT04037085 and FDAAA801

STUDY TITLE:

**Ketamine to Improve Recovery After Cesarean
Delivery – Part 1**

(KINETIC)

VERSION 2.0

DOCUMENT DATE: 11/20/2022

I. Clinical Protocol

In a prospective, open label, observational design study, women who were weaning from breastfeeding were enrolled. Women were included if they were ≥ 18 years of age, able to provide informed consent, weaning from breastfeeding, ASA physical status 1, 2, or 3, and producing a minimum of 2mL breast milk every 24 hours. They were excluded if they were allergic to study medications, ASA physical status 4 or greater, had a history of psychiatric comorbidity, uncontrolled hyperthyroidism, cardiac disease, fever, hypertension, history of hallucinations, alcohol, or illicit substance abuse, were on chronic opioid therapy, or had chronic pain disorders.

II. Dose Administration

Subjects received a sub-anesthetic ketamine infusion at 0.1 mg/kg/hour for 12 hours (not to exceed 8mg/hr dose). The justification for intravenous administration for 12 hours of 0.1mg/kg/hr are based on pharmacokinetic studies in humans¹⁸⁻²⁰. Ketamine produces analgesia at plasma concentrations of 100-200ng/mL, which is a fraction of the plasma concentrations associated with general anesthetic doses (9000-25,000 ng/mL)^{18,19}. In longitudinal studies reporting ketamine infusions from 0.05 -1mg/kg/hr, significant reductions in pain scores with minimal adverse events and no psychomimetic effects were observed over infusions lasting up to 5 days, while the effect of ketamine on pain scores were notably varied according to infusion duration^{21,22}.

III. PK Sampling Schedule of Treatment Group

Blood samples (2-3mL each) were collected at 8, 10, 12, 12.5, 13, 14, 16, and 20 hours after ketamine infusion start. Plasma was obtained by centrifugation at room temperature and kept frozen until analysis. The entire human milk expressed was collected starting at the time of infusion initiation (t_0) and ending 12 hours after the infusion was stopped (t_{24}). Breastmilk was labeled by collection time and weighed to estimate the volume (1 gram = 1 mL) and stored at -80°C until analysis. Patient vital signs were monitored every hour and continuous pulse oximetry was done for 12 hours during the infusion and for 12 hours after infusion.

IV. Analytic Methods: Liquid Chromatography-tandem Mass Spectrometry (LCMS/MS) Assay for Ketamine and Metabolites in Breast

Samples were separated using a Waters UPLC equipped with Acquity UPLC BEH RP18 $1.7\mu\text{m}$, 2.1×100 mm column combined with a guard filter (Waters # 289002078). The Liquid Chromatography (LC) method consisted of a gradient mobile phase of Solvent A (95% 2mM Ammonium Acetate + 5%

Acetonitrile + 0.1 % Formic Acid) and Solvent B (95% Acetonitrile and 5% Water) for elution of the analyte. The gradient started at 100% of Solvent A which was held for 1.0 minute and then changed to 80% Solvent A and 20% Solvent B which was kept constant for the next 3 minutes. The solvent composition then changed to 65% Solvent A and 35% Solvent B over 0.1 min and then immediately to 30% Solvent A and 70% Solvent B which was maintained for 1 minute. The gradient then returned to the initial solvent condition of 100% Solvent A, achieving the initial base line. The total run time was 7 minutes with a flow rate of 0.3 mL/min.

Analysis was performed on a Waters TQ-S Mass Spectrometer (Waters, Milford, MA) in positive electron spray mode (+ESI) using multiple reaction monitoring (MRM). The following MRM settings were employed: Capillary Voltage 1.5kV, de-solvation temperature 500°C, Cone gas flow 150 L/h, de-solvation gas flow 1000 L/h; Argon pressure 0.15 mL/min, Nitrogen pressure 7 bar and dwell time was 0.038 sec. The extracted ions following MRM transitions monitored were m/z 237.84→124.994 for KET, m/z 223.9→125.01 for NKET, m/z 221.9→141.83 for DHNK, m/z 241.9→128.91 for KET-D₄ (IS for KET and DHNK) and m/z 227.9→128.96 for NKET-D₄ (IS for NKET). The LC and mass spectrometer were controlled, and data collected using Masslynx® software version 4.2 (Waters Corporation, Milford MA).

Ketamine (KET) and its metabolites (NKET & DHNK) were analyzed in plasma and breast milk samples using ultra high-pressure liquid chromatography and mass spectrometric analysis. The developed assay was linear between 0.05 - 100 ng/ml and Coefficient of Variability (CV) of the assay was less than 10%.

V. PK Calculations

The pharmacokinetic parameters were calculated using Phoenix™ WinNonlin 8.3.4 (Certara, Princeton NJ). A two compartment PK model was used to estimate PK parameters of ketamine. These parameters included Area Under the Curve (AUC) estimates, the elimination half- life ($t_{1/2}$), clearance (CL), Area Under Moment Curve (AUMC), Mean Residence Time (MRT) and Volume Distribution Steady State (V_{dss}). Statistics will include Mean, Standard deviation (SD), and range where applicable.

- a. **Area Under the Curve (AUC)** is defined as the area under the concentration-time curve. AUC was calculated by linear trapezoidal method.
- b. **Elimination half-life ($t_{1/2}$)** is the time required for drug concentration to decrease by one-half at the end drug dosing. Elimination half-life was obtained from the slope of terminal elimination phase.
- c. **Clearance (CL)** is calculated as the Dose/ $AUC_{0-\infty}$ and calculated by Phoenix WinNonlin.

- d. **Volume Distribution Steady State (Vdss)** is the period of dynamic equilibrium of the drug calculated as the amount of drug in the body at time, t divided by the plasma concentration of the drug at time, t. These data were calculated by Phoenix WinNonlin.
- e. **Metabolic ratio** was calculated for each metabolite using the formula:

$$\text{Metabolic ratio} = \frac{\text{Metabolite } AUC_{0-\infty}}{\text{Parent } AUC_{0-\infty}}$$

VI. Milk to Plasma Ratio

Milk to plasma ratio for KET, NKET, and DHNK were calculated by dividing the concentration of the respective components Ketamine and Ketamine metabolites in human milk by plasma concentration at the corresponding times (± 30 min). Ratios higher than 1 indicate breastmilk concentrations of ketamine and the metabolites would be higher in breastmilk than in maternal plasma concentrations.

VII. Relative Infant Dose (RID) Calculations

The relative infant dose was calculated from the concentrations of ketamine and its metabolites in breast milk at different times following ketamine administration to the women. The concentration of ketamine and its metabolites were converted to amount by multiplying with the volume of breast milk collected at various time intervals. The cumulative dose of ketamine and molar equivalents of metabolites was calculated and RID was calculated using the formula²³⁻²⁵: An RID $\leq 10\%$ was considered low²⁴.

$$RID (\%) = \text{Cumulative infant dose via breast milk} \left(\frac{\text{mg}}{\text{kg}} \right) \times 100 \div \text{maternal dose} \left(\frac{\text{mg}}{\text{day}} \right)$$

VIII. Descriptive Statistics

Descriptive Statistics will include participant characteristics such as maternal age, maternal race, gravida, parity, ASA rating, and weight. Means and standard deviations (SD) are calculated for maternal age and weight. Medians and range are used for maternal gravida, parity, and ASA rating. Maternal race is noted as a proportion of the total sample.

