OR Women who are weaning from breastfeeding. We will use multiple recruitment methods which are shown in the recruitment section. The women will come into the CTRC in Montefiore to provide consent. Interested patients will be provided with a full explanation of study-related goals and procedures. The informed consent document will be reviewed in its entirety with the potential subject. All questions will be answered to the subjects' satisfaction. The patient may decide on participation in the study at any time during or after the initial encounter. The study coordinator or investigators can be contacted after the subject makes a volitional decision to participate in the study. The physician investigators will obtain written informed consent. The consent will be provided by the patient themselves; no patients will be approached or recruited if they are unable to consent for themselves. A study physician will perform a history and physical and confirm ASA inclusion criteria after consent on day of study drug administration. For this weaning population, a urine pregnancy test will be performed the morning of CTRC visit, after informed consent and prior to any study related procedures. A positive test allows

the PI or CO-Is to re-evaluate the participants eligibility for this study. Subjects will not be informed of the outcome of the study at this time except through routine reporting structures available to the public forum via ClinicalTrials.gov. The CTRC has 24/7 RN staff and it will be a 1:1 participant:RN ratio. All staff are trained on IV ketamine protocol. They will be discharged after 24 hours after the start of infusion or as seen medically fit by the discharging physician.

Ketamine will be delivered in an open-label fashion as follows: 0.1mg/kg/hr IV infusion after cord clamping or at CTRC at a scheduled time with the participant and clinic (maximum allowable dose 8mg/hr infusion rate), for a total duration of 12 hours. Pharmacokinetic studies will be performed on breastmilk, serum, and urine samples.

Blood samples: 3mL whole blood at each sample from an indwelling intravenous catheter or by fresh sample by 25g or smaller butterfly needle. Specimens will be placed on ice and stored within 24 hours at -20 to -80C until analysis. Timepoints for collection: 8-10hrs into study drug infusion; 12hrs into study drug infusion; after infusion end at the following times: 0.5hrs, 1hr, 2hr, 4hr, 8hr, 24hr.

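### SAP V names two sources for ketamine AUC; if the linear trapezoid is used from zero to the first sample at 8 h, AUC0-inf is too low and clearance too high

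*SAP*

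**What the plan says.** SAP V (PK Calculations) opens with "A two compartment PK model was used to estimate PK parameters of ketamine" and lists AUC and clearance (CL) among those parameters. The lettered items then describe the calculations:

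- Item a: "AUC was calculated by linear trapezoidal method".
- Item b: "Elimination half-life was obtained from the slope of terminal elimination phase".
- Item c: clearance "is calculated as the Dose/ $AUC_{0-\infty}$ and calculated by Phoenix WinNonlin".
- Item e: the metabolic ratio "was calculated for each metabolite using the formula" of metabolite AUC0-inf over parent AUC0-inf.

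The model is stated for ketamine only. For the metabolites, item a is the only AUC method given. Nothing says which AUC feeds items c and e, how the interval from 0 to 8 h is handled, or how the area beyond the last sample is added.

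SAP III fixes the plasma times: "Blood samples (2-3mL each) were collected at 8, 10, 12, 12.5, 13, 14, 16, and 20 hours after ketamine infusion start". The Protocol (Methods, blood samples) also starts late, "Timepoints for collection: 8-10hrs into study drug infusion; 12hrs into study drug infusion", but its last sample is 24 h after the infusion ends, that is, 36 h after it starts. The results are summarised as "Statistics will include Mean, Standard deviation (SD), and range where applicable", and the Protocol's target is 6 complete women.

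**The concern.** A model-based AUC and a trapezoidal AUC are different estimates, and with this sampling scheme they can differ materially. Under constant-rate input the concentration rises in a concave curve. With no sample before 8 h, the trapezoid has to bridge two thirds of the infusion with one straight line. Joined from zero, that line lies below the curve, so AUC is understated and Dose/AUC0-inf overstated.

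Aim 2 of the Protocol is to quantify ketamine pharmacokinetics. An error in the same direction in every woman is not removed by averaging over six. It need not cancel in the metabolic ratio either, because parent and metabolite rise with different shapes over 0-8 h. As written, a reader cannot tell how the reported CL or the ratio was obtained.

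**Working it through.** **Inputs from the documents.** A 12 h infusion at constant rate (SAP II); plasma at 8, 10, 12, 12.5, 13, 14, 16 and 20 h (SAP III); CL = Dose/AUC0-inf (SAP V.c). The plan states no AUC, CL or half-life, so there is no figure of its own to reproduce.

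**Assumed.** All half-lives; C(0) = 0 joined to C(8); tail = C(20)/lambda, with lambda the log-linear slope through 14, 16 and 20 h.

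**Formulas.** With concentration in units of the steady-state level Css, each exponential phase contributes a share f of AUC at rate k = ln 2/half-life. During infusion, C(t) = sum of f(1 - e^(-kt)). The true AUC0-inf is 12 (in Css x h).

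**Two worked cases:**

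| | One compartment, 2.5 h | Two compartments, 0.25 h and 3 h, 30% of AUC in the fast phase |
|---|---|---|
| C(8) | 0.891 | 0.890 |
| True AUC0-8 | 4.786 | 5.339 |
| Straight line, 8 x C(8)/2 | 3.565 | 3.559 |
| Loss over 0-8 h, share of 12 | 10.2% | 14.8% |
| Trapezoid 8-20 h (true) | 6.934 (6.836) | 6.291 (6.213) |
| Tail beyond 20 h (true) | 0.378 (0.378) | 0.447 (0.447) |
| Estimated AUC0-inf / 12 | 0.906 | 0.858 |
| CL / true CL | 1.103 | 1.165 |

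The trapezoid overstates the convex decline after 12 h, but this gives back less than 1% of AUC.

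**Ranges at the SAP's times.**

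- Two-compartment grid of 92 sets (fast half-life 0.25-2 h, terminal 2-12 h, fast share 15%-70%): AUC 0.753-0.946 of truth, CL 1.057-1.327, low AUC in all 92.
- A second grid of 324 sets (fast 0.1-1 h, terminal 2-16 h, fast share 5%-70%): CL 2.1%-39.4% too high, low AUC in all 324.
- One compartment, half-life 1-12 h: CL from 25.9% too high at 1 h down to 0.9% at 12 h.

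**Where the loss arises (92 sets).** The 0-8 h line removes 2.7%-25.1% of AUC. Tail extrapolation removes 0%-13.7% and is more than half the shortfall in 9 sets, all with terminal half-life 8 or 12 h.

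**Dependence on time 0.** If C(8) is carried back flat to time 0, the second worked case gives (7.118 + 6.291 + 0.447)/12 = 1.155, and AUC is too high in 91 of the 92 sets, by up to 20%.

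**Dependence on the last sample.** With Protocol times (first sample at 8 h, last at 36 h), AUC is 0.76-1.00 of truth on the 92 sets and 0.80-1.02 for one compartment.

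**Metabolic ratio.** The metabolite was taken as one compartment formed from ketamine, half-life 1-6 h, on the same 92 sets. If both AUCs are trapezoidal, the 0-8 h line alone overstates the ratio by 3%-32%. If only the metabolite AUC is trapezoidal, the line alone gives 0.86-1.02 times the true ratio. Tail error comes on top and can go either way; it is hard to bound when the metabolite is still near its plateau at 20 h.

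**The case against.** The strongest reply is that SAP V has already answered the question. Its lead sentence attributes AUC and CL to the fitted model. In a linear two-compartment model CL = Dose/AUC0-inf is an identity, so item c is consistent with a fit, and a terminal-slope half-life (item b) is compatible with the model's terminal phase. On that reading only item a is out of place, and ketamine CL carries no trapezoid bias. This stands. It leaves item a to be corrected and the metabolite AUC0-inf with no stated method but the trapezoid.

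A reader might infer more than the documents support:

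- **That the reported CL is known to be biased.** The SAP does not say that the trapezoidal AUC feeds item c, so the bias is conditional.
- **That the direction is certain.** It needs C(0) = 0 joined to C(8), or no area counted before 8 h. Zero is the natural value before an infusion, but the SAP does not state the handling, and a flat carry-back reverses the sign. The Protocol's 36 h sample also weakens it.
- **That a typical error can be given.** A median over a grid reflects the grid. A smaller assumed fast-phase share gives a smaller bias.
- **That a mean of six women would almost surely be too high.** That holds only if all six share the same kinetics. Between-woman variation can hide the bias in a sample of six, though it does not remove it.

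**Conclusion.** The conflict between the lead sentence of SAP V and item a is in the text and needs no assumption. So is the absence of any method other than the trapezoid for the metabolite AUC0-inf.

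The bias is conditional. If the trapezoid feeds Dose/AUC0-inf with zero at time 0, AUC0-inf is too low and CL too high at the SAP's times, in every two-compartment set tried and in one-compartment cases. The sizes in the brief paragraph and the working rest wholly on assumed half-lives. If the fit supplied the ketamine values, the bias is absent for them, and the metabolic ratio divides a trapezoidal AUC by a model-based one.

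The harm is confined to descriptive Aim 2 estimates and the metabolic ratio, and no test or threshold uses them. A reader might take the bias to reach the breastfeeding conclusions. It does not: milk concentration (the primary outcome), the milk-to-plasma ratio (SAP VI) and the relative infant dose (SAP VII) do not use plasma AUC. The point should be fixed, and confidence is higher in the ambiguity than in the size of any bias.

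**What to change.** In SAP V.a, V.c and V.e, name one source for each parameter, and do not use a straight line over 0-8 h for any AUC0-inf, CL or metabolic ratio.

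1. **Ketamine.** Take AUC0-inf and CL from the two-compartment fit with the recorded infusion as zero-order input, and report parameter precision for each woman. If this was already done, correct only item a for ketamine.
2. **Metabolic ratio.** Use the same method for parent and metabolite: a joint parent-metabolite fit, or a superposition fill of 0-8 h from the post-infusion samples. The fill is C(s) = C(12) - C(12+s) + [C(8) + C(20) - C(12)] x s/8 at s = 0.5, 1, 2 and 4 h, followed by the trapezoid. It assumes linear kinetics and a constant rate. The Protocol's vital-signs paragraph allows for a rate increase; where the rate changed, fit with the recorded rates instead.
3. **Tail.** State which last sample was used, reconciling the SAP's 20 h with the Protocol's 36 h, and report the share of AUC extrapolated beyond it.
4. **Sensitivity analysis.** Show the superposition-filled non-compartmental value beside the fit, especially where a single-woman fit is imprecise.

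The cost is wording and a rerun on existing data, with no new samples. Some single-woman fits will be imprecise: with 10% noise in six assumed sets, the root mean squared error of fitted CL (relative to truth) was 0.06-0.27, against 0.13-0.24 for the trapezoid. The fill does not repair the tail. Without noise, on the 92 sets, its CL is within 4% of truth for terminal half-lives up to 6 h but up to 16% too high overall.

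### The metabolic ratio in SAP V.e needs AUC0-∞, but plasma is drawn only from 8 to 20 h, and the SAP does not say how the unobserved parts of each AUC are obtained

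*SAP*

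**What the plan says.** SAP V.e defines the ratio, for each metabolite, as metabolite AUC0-∞ over parent AUC0-∞: "Metabolic ratio} = \frac{\text{Metabolite } AUC_{0-\infty}}{\text{Parent } AUC_{0".

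SAP III gives the plasma times: "Blood samples (2-3mL each) were collected at 8, 10, 12, 12.5, 13, 14, 16, and 20 hours after ketamine infusion start". The infusion lasts 12 h, so the first draw comes 8 h into it and the last 8 h after it ends. Protocol Methods 1 also has no draw before 8 h, but it lists one 24 h after infusion end (36 h after the start). The SAP schedule does not contain that draw. The same protocol section discharges weaning women at about 24 h after the start.

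On method, SAP V says "A two compartment PK model was used to estimate PK parameters of ketamine" and continues "These parameters included Area Under the Curve (AUC) estimates". Item a then says "AUC was calculated by linear trapezoidal method", and item b says "Elimination half-life was obtained from the slope of terminal elimination phase". No model is named for norketamine (NKET) or DHNK. Nothing is said about how 0-8 h is filled, which points define the terminal slope, how much of an AUC may be extrapolated, or what happens if the slope is not falling. Results are summarised as "Statistics will include Mean, Standard deviation (SD), and range where applicable".

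**The concern.** An AUC from zero to infinity built on an 8-20 h window has two constructed ends, and they do not cancel in a ratio because they fall differently on parent and metabolite. The plan leaves open which method supplies each end, and the choice changes both the size and the sign of the error.

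With a target of 6 women and a summary by mean, SD and range, one largely extrapolated value counts as much as a well-observed one, and a reader cannot tell them apart. The stake is the description of metabolite exposure under Aim 2.

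**Working it through.** The documents give no AUC, half-life or ratio, so there is no plan figure to reproduce. What follows takes the sampling times and infusion length from SAP II and III and the AUC rules from SAP V. **Every half-life is an assumption.**

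**Ordering of the gaps.** Under linear kinetics, a metabolite formed only from ketamine has a curve that is the ketamine curve delayed. Its share of AUC before 8 h is therefore smaller than ketamine's, and its share after 20 h larger, whatever the half-lives.

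**Model.** Scale each true AUC0-∞ to 1. For elimination rate k = ln 2 / half-life:
- F(t; k) = (1 − e^(−kt))/12 up to 12 h, then F(12; k)·e^(−k(t−12)).
- Ketamine (rate p) is F(t; p).
- A one-phase metabolite (rate m) is [m·F(t; p) − p·F(t; m)]/(m − p).

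**Estimate.** Straight line from zero at 0 h to the 8 h value (assumed), linear trapezoids to 20 h, then C20/λ with λ from the log slope of the last three points (assumed). Because true AUCs are 1, estimated/true ratio = metabolite estimate / ketamine estimate.

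**One worked case: ketamine 3 h, metabolite 6 h.** The metabolite curve is 2F(t; 6 h) − F(t; 3 h).

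| | 0-8 h | 8-20 h | beyond 20 h | sum |
|---|---|---|---|---|
| Ketamine, true | 0.363 | 0.584 | 0.053 | 1 |
| Ketamine, estimated | 0.2808 | 0.5907 | 0.0533 | 0.9248 |
| Metabolite, true | 0.100 | 0.523 | 0.376 | 1 |
| Metabolite, estimated | 0.1213 | 0.5211 | 0.7364 | 1.3788 |

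Estimated/true = 1.3788/0.9248 = 1.49, or 1.38 with an exact ketamine AUC. The metabolite is close to its peak at 14 h, so the slope over 14, 16 and 20 h gives a half-life of 13.7 h instead of 6 h. The extrapolated part is 0.7364/1.3788 = 53% of the estimate.

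**Ranges.** One-phase set: ketamine 2 to 4 h by 0.5 h, metabolite 2 to 8 h by 1 h (35 scenarios). Slow-phase set: ketamine 2, 3, 4 h; metabolite fast phase 1, 2, 3 h and slow phase 8, 12, 24 h carrying 20, 30, 50 or 70% of its AUC (108 scenarios).

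| | One-phase | Slow-phase |
|---|---|---|
| Ketamine AUC beyond 20 h | 1.5-10.5% | 1.5-10.5% |
| Metabolite AUC beyond 20 h | 7-52% | 10-63% |
| Extrapolated part of estimated metabolite AUC, median | 45% | 30% |
| Estimated/true, trapezoids for both | 1.14-2.75 | 0.73-1.56 |
| Scenarios below 1 | 0 of 35 | 32 of 108 |
| Estimated/true, exact one-compartment ketamine AUC | 1.02-2.61 | 0.64-1.48 |
| Scenarios below 1 | 0 of 35 | 63 of 108 |
| Trapezoids for both, 36 h draw added | 1.08-1.22 | 0.89-1.20 |

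The 32 trapezoid values below 1 split by slow half-life as 0 of 36 (8 h), 7 of 36 (12 h, lowest 0.957) and 25 of 36 (24 h). With an assumed two-compartment ketamine and its exact AUC, the ranges are 1.00-1.87 and 0.63-1.30.

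**0-8 h gap alone.** With exact tails and trapezoids for both, the one-phase ratio is 1.07-1.16 times true. The straight line cuts ketamine's early area, leaving its total AUC at 0.88-0.95 of true.

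**Metabolite formed from a metabolite.** If DHNK forms from NKET (assumed), a chain of 3, 6 and 6 h is still rising at 20 h, so AUC0-∞ cannot be computed. In a wider set (NKET 2-6 h, DHNK 1-8 h), 70 of 180 scenarios had no falling slope.

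**Assay noise.** SAP IV states that the "Coefficient of Variability (CV) of the assay was less than 10" percent. At 5% CV, the 95th/5th percentile of one woman's AUC0-∞ ratio has a median of 1.43 (one-phase) and 1.20 (slow-phase), against 1.09-1.10 for an AUC8-20h ratio. Replicates without a falling slope were removed.

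**The case against.** The best defence is that the ratio has no test, threshold or decision attached, the protocol does not name it, and its sole listed outcome is milk concentration. That stands and sets the severity. It is also fair that the sizes rest on assumed half-lives, a zero at 0 h and a three-point slope. Using the last two points for the metabolite lowers the one-phase maximum from 2.75 to 1.91. A two-compartment ketamine fit would also fill ketamine's early gap. None of this tells the reader which AUC enters V.e or how a metabolite's ends are obtained.

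Three stronger readings are tempting, and the documents do not support them:
- **That metabolite AUCs are less well observed overall.** This is true of the tail only. Ketamine has the larger 0-8 h gap, and in a wider set of assumed kinetics the total unsampled area was larger for the metabolite in only 31-64% of scenarios.
- **That the direction of error cannot be known at all.** With trapezoids for both analytes it is usually upward: all 35 one-phase and 76 of 108 slow-phase scenarios. Values below 0.95 need an assumed 24 h phase, which nothing in the documents supports. The sign is open mainly because V does not settle the source of ketamine's AUC.
- **That the milk results or RID are affected, or that 36 h samples were taken and left out.** The ratio feeds neither the milk-to-plasma ratio nor RID, and the documents do not show whether 36 h samples exist.

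**Conclusion.** The point holds as a low-severity defect in a secondary descriptive quantity. V.e asks for AUC0-∞ from an 8-20 h window and leaves the AUC source ambiguous for ketamine and without a model for the metabolites.

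The ordering of the two gaps needs only linear kinetics and formation from ketamine alone. The sizes are conditional on the assumed half-lives and estimation rules. Trapezoids for both analytes usually overstate the ratio, by a factor of up to 2.75 in the one-phase set. With a model-based ketamine AUC and a trapezoidal metabolite AUC, the error can go either way, depending on whether the metabolite has a slow phase. For DHNK the quantity may not be estimable by 20 h.

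**What to change.** 1. Use one AUC method for parent and metabolite in V.e and name it. Do not fill 0-8 h with a straight line from zero.
2. Report the terminal points and percent extrapolated for each woman and analyte. Where the slope is not falling, report AUC0-∞ as not estimable.
3. Report alongside it metabolite AUC8-20h over ketamine AUC8-20h in molar units, labelled as an observed-window ratio and not total exposure. V.e names no unit, while SAP VII uses molar equivalents. The m/z values in SAP IV imply factors of 237.84/223.9 = 1.06 (NKET) and 237.84/221.9 = 1.07 (DHNK).
4. Reconcile the protocol's 36 h draw with the SAP's last draw at 20 h and the discharge at about 24 h. If 36 h samples exist, use them in V.e; if not, say so.

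Any limit on extrapolation, such as 20% (not a figure from the documents), should flag values and not exclude them: only 4 of 35 and 25 of 108 scenarios meet it.

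The cost is SAP wording and recalculation on existing data, with no new draw. A metabolite model fitted to draws that start at 8 h will rest on assumptions that must be stated. The window ratio is a different quantity: 0.53-1.22 times the total-exposure ratio across both sets, and 0.37-1.28 in 45 scenarios with DHNK formed from NKET.

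### SAP VI pools same-time milk/plasma ratios from during and after the infusion and plans no AUC-based ratio, so slow milk re-equilibration could make post-infusion ketamine ratios read high

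*SAP*

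**What the plan says.** SAP VI divides the concentration of ketamine and each of two metabolites "in human milk by plasma concentration at the corresponding times (± 30 min"). Its one sentence of interpretation is "Ratios higher than 1 indicate breastmilk concentrations of ketamine and the metabolites would be higher in breastmilk" than in plasma. It does not distinguish times during the infusion from times after it.

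SAP III describes the samples. Plasma samples "were collected at 8, 10, 12, 12.5, 13, 14, 16, and 20 hours after ketamine infusion start". For milk, "The entire human milk expressed was collected starting at the time of infusion initiation", continuing to 24 h, and "Breastmilk was labeled by collection time and weighed to estimate the volume". SAP III lists no milk times. The protocol (Methods 1, breastmilk) also collects the total expressed volume. It schedules 0-2, 4, 8 and 12 h, then 2, 4, 8 and 24 h after the infusion ends.

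SAP V plans AUCs ("AUC was calculated by linear trapezoidal method") and a metabolic ratio that "was calculated for each metabolite using the formula" of metabolite AUC over parent AUC. Nowhere does the SAP plan a milk AUC or a milk/plasma AUC ratio.

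**The concern.** The numerator and denominator of the ratio can refer to different times. A whole expression may carry drug from the entire interval since the last one, while plasma is measured at one moment. While plasma ketamine rises, a lagging milk concentration makes the ratio read low. Once the infusion stops and plasma falls, the same lag makes it read high.

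On the protocol milk times and SAP plasma times, three of the five available pairs fall after the infusion stops. Part 1 is meant to inform whether a later trial excludes or permits breastfeeding dyads. A reader who sees post-infusion ratios above 1 could take them as evidence of extensive transfer into milk when they may only show milk trailing behind plasma.

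**Working it through.** The documents state no ratio, half-life or exchange rate, so there is no planned figure to reproduce. What follows is an illustration under stated assumptions.

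**Pairs.** Protocol milk times up to 24 h are 0-2, 4, 8, 12, 14, 16 and 20 h. SAP plasma times are 8, 10, 12, 12.5, 13, 14, 16 and 20 h. Within 30 minutes these pair at 8, 12, 14, 16 and 20 h.

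**One worked case.** Assume a true ratio of 1, one-compartment plasma with a 3 h half-life (k = ln 2/3 = 0.2310 per h), complete emptying at each expression, and no exchange between stored milk and plasma. In units of steady state, C(t) = 1 - exp(-kt) up to 12 h, then C(12)·exp(-k(t-12)). Milk at each expression is the mean of C since the previous one.

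- After the stop, milk/plasma = (exp(kd) - 1)/(kd) for an interval of d hours. For d = 2 (14 and 16 h): (1.587 - 1)/0.4621 = 1.27. For d = 4 (20 h): (2.520 - 1)/0.9242 = 1.64. The mean of the three is about 1.40.
- At 8 h: milk = 1 - (0.3969 - 0.1575)/0.9242 = 0.741; plasma = 0.8425; ratio 0.88.
- At 12 h: milk = 1 - (0.1575 - 0.0625)/0.9242 = 0.897; plasma = 0.9375; ratio 0.96.
- Linear trapezoid, 8-20 h. Milk at 8, 12, 14, 16, 20 h is 0.741, 0.897, 0.751, 0.473, 0.243, giving 3.276 + 1.648 + 1.224 + 1.431 = 7.58. Plasma at its eight times gives 1.743 + 1.838 + 0.443 + 0.395 + 0.667 + 0.963 + 1.039 = 7.09. Ratio 7.58/7.09 = 1.07.

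**Range for ketamine.** The same model was run on 20 assumed plasma curves: one-compartment half-lives of 2, 3, 4 and 5 h, and two-compartment curves with a rapid phase of 0.25 or 0.5 h carrying 30% or 50% of steady state and a terminal half-life of 2-5 h. True ratio 1, complete emptying.

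| Exchange half-life | 14 h | 16 h | 20 h | 8-20 h trapezoid AUC ratio |
|---|---|---|---|---|
| No exchange | 1.15-1.89 | 1.15-1.50 | 1.34-2.17 | 1.02-1.15 |
| 2 h | 1.12-1.66 | 1.12-1.39 | 1.21-1.70 | 1.02-1.13 |
| 0.5 h | 1.07-1.33 | 1.07-1.21 | 1.09-1.25 | 1.02-1.09 |
| Near-instant (0.05 h) | 1.01-1.03 | 1.01-1.03 | 1.01-1.02 | 1.00-1.06 |

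During the infusion this model gives 0.83-1.00 at 8 h and 0.92-1.00 at 12 h. If 30% of milk stays in the breast and there is no exchange, post-stop ratios run 1.13-4.06.

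**A different milk model.** Treating milk as a first-order compartment lagging plasma (five assumed curves, half-lives 2-5 h) gives the following at 14, 16 and 20 h. Equilibration half-time 1 h: 1.15-1.69, 1.22-1.75, 1.25-1.94. At 2 h: 1.13-1.97, 1.31-2.32, 1.51-3.71. At 0.25 h the excess at 14-20 h is only 5-14%. The one post-stop value below 1 is 0.97 at 14 h (plasma half-life 5 h, equilibration 4 h). Ratios at 8 and 12 h are 0.88-0.98 at 1 h and 0.73-0.93 at 2 h.

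**Does the AUC ratio help?** On the 20 ketamine curves, the 8-20 h trapezoid was closer to the true ratio than the mean post-stop ratio in 20 of 20 under both milk models, unless exchange was near-instant (4 or 5 of 20). It is not exact: the lag model gives 1.04-1.23, 1.02-1.35 and 0.89-1.34 at equilibration half-times of 1, 2 and 4 h. One reason is the window. Plasma sampling starts at 8 h, so the rise is left out while the fall is kept. Under the five curves above, 31-49% of plasma AUC from 0 to 20 h lies before 8 h.

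For metabolites (nine assumed curves, half-lives 5-12 h), the trapezoid was closer in at most 3 of 9.

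**The case against.** SAP VI makes no false statement. It defines a time-matched ratio, and its sentence about ratios above 1 is literally true of measured concentrations. It never calls the ratio a measure of transfer. No threshold or decision rule is attached to it. The primary outcome is the concentration in milk, and the relative infant dose uses amounts "converted to amount by multiplying with the volume of breast milk collected at various time intervals". All this stands and keeps the point minor.

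Every kinetic value above is assumed, and the five pairs combine protocol milk times with SAP plasma times. Actual expression times may differ. That also stands: the direction is conditional and the size unknown.

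The AUC ratio has limits too. It gains nothing when exchange is near-instant and is not shown to be better for metabolites. It may be unavailable for women with few expressions, given the 2 mL per 24 h entry minimum and a target of six complete participants. The SAP reports collection and calculation in the past tense, so this would be an added descriptive summary. These limits narrow the remedy to ketamine, beside the existing ratios. They do not answer the pooling of during- and post-infusion times or the lack of any caution about lag.

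**Conclusion.** The point holds as a modest, conditional gap in a descriptive summary. If milk re-equilibrates slowly, post-infusion ketamine ratios can read above the true ratio and during-infusion ratios below it. For a true ratio of 1 with complete emptying, the whole-expression model puts the post-stop ratio anywhere from 1.01 to 2.17, depending on assumed half-life and exchange rate. The lag model can give more. The documents cannot say where in that range this study lies, and the bias may be nil.

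A reader might infer three stronger things that the documents do not support:

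- That the trial's main conclusions are biased. They are not affected by this ratio, because neither the primary outcome nor the relative infant dose uses it.
- That an AUC ratio is the correct answer for every compound. The advantage was seen only for ketamine and only without near-instant exchange.
- That the AUC ratio's error can be bounded. The ranges change with the assumed milk model.

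**What to change.** In SAP VI:

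1. Report ratios during the infusion (nominally 8 and 12 h) separately from those after it (nominally 14, 16 and 20 h).
2. After the sentence on ratios above 1, add that a post-infusion ratio above 1 may reflect milk lagging behind falling plasma and is not by itself a measure of transfer.
3. For ketamine only, also report AUCmilk/AUCplasma for each woman, by the linear trapezoid already used in SAP V, over the window shared by her recorded milk and plasma times (nominally 8-20 h if the protocol milk times were followed). Place it beside the time-specific ratios and give the number of women evaluable.
4. State that this AUC ratio is partial, because plasma sampling starts at 8 h and the rise is omitted.

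Do not write numeric error bounds into the SAP, since they would rest on assumed kinetics. Do not add a sensitivity version that sums concentration times collection interval: with near-instant exchange it reads 0.86-0.94 when the truth is 1, while the same-time ratios after the stop read 1.01-1.03.

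The cost is some SAP wording and one recalculation from existing samples and recorded times. Nothing is removed. The downside is one extra descriptive ratio, unavailable for women with sparse expressions and uninformative if exchange is near-instant.
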